 initiated at a total daily dosage of 10 mg/kg per day.

Study design:

Type of the study: randomized controlled study.

The following data will be gathered and evaluated for all patients:

I-before intervention:

- Serum creatinine, Creatinine clearance. .1
- 24 hour urine protein, urine protein/creatinine ratio. .2
 - Urine analysis. .3
 - HBA1c. .4
 - HGB. .5
 - Uric acid and lipid profile. .6
 - Lupus serology. .7

II-after intervention: All patients will be evaluated monthly regarding:

- Serum creatinine, creatinine clearance. .1
- 24 hour proteinuria, protein/creatinine ratio. .2
- Fasting, random and postprandial glucose levels. .3
 - CNI trough level if used. .4
 - Urine analysis. .5
 - HGB level. .6
 - Uric acid, lipid profile. .7
 - Lupus serology. .8

Cardiovascular assessment: .9

ECCHO.

Atherosclerosis and vascular calcification incidence (NCCT model).

Regular measurement of blood pressure each visit.

Outcomes:

- Effect of dapagliflozin compared to placebo on eGFR. .1
- Effect of dapagliflozin compared to placebo on systolic/diastolic blood .2 pressure.
 - Effect of dapagliflozin compared to placebo on body weight. .3
- Safety of dapagliflozin vs. placebo the number of hypoglycemia .4 episodes between groups and serious adverse events.

Statistical Analysis:

Qualitative data were displayed in cross tabulations, and quantitative data were described in terms of arithmetic mean ± SD. Bivariate techniques were used for initial evaluation of contrasts. Thus, the chi-square and Fisher's exact tests were used for comparisons of frequencies of qualitative variables; the Mann-Whitney test and the unpaired t-test were used for comparisons of means of two quantitative variables. A p-value <0.05 was considered significant. Graft and patient survival rates were assessed using the Kaplan-Meier method. All analyses were carried out using the computer package SPSS for windows, release 16 SPSS Inc. Chicago, III, USA.

Administrative design •

Informed consent will be obtained from all subjects and the approval will be obtained from institutional review board (IRB) in Faculty of Medicine, Mansoura University. There is no funding.

Research question

The main research question is: Does use of SGLT2i will show superiority over conventional lines of treatment of lupus nephritis patient as regard efficacy and safety.

Rationale and justification

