
General Considerations

Significance Level: A two-sided alpha level of 0.05 will be used for all primary analyses.

Analysis Populations:

Intent-to-Treat (ITT): All randomized patients will be analyzed according to their assigned group.

Per-Protocol (PP): Only patients completing the study without major protocol violations.

Primary Endpoint Analysis

Renal Outcomes: ANOVA for repeated measures for serum creatinine and eGFR if normally distributed, and the Friedman test for non-normally distributed data. Post-hoc tests using Bonferroni correction.

Cardiovascular Outcomes: Mann-Whitney U test for BNP levels and coronary calcification between groups.

Hematological Outcomes: Paired t-test for hemoglobin and erythropoietin levels if data is normally distributed; otherwise, Wilcoxon signed-rank test.

Secondary Endpoint Analysis

Body Weight and BMI: Compared over time using ANOVA for repeated measures.

Echocardiographic Parameters: Analyzed with paired t-tests, adjusted with Bonferroni correction.

Iron Profile: Analyzed pre- and post-intervention using ANOVA or Kruskal-Wallis for non-normally distributed variables.

Categorical Variables

Chi-Square Test: For between-group comparisons of categorical data (e.g., presence of diabetes, hypertension).

7. Handling of Missing Data

Imputation: Last observation carried forward (LOCF) for data missing at random; multiple imputation for extensive missing data.

Sensitivity Analysis: Conducted to evaluate the robustness of primary endpoint findings against different missing data assumptions.

8. Interim Analysis

Timing: An interim analysis is planned at the halfway point (6 months).

Stopping Rules: An O'Brien-Fleming approach will be applied to adjust the significance threshold for interim testing, allowing for an earlier stop for efficacy or safety concerns.

9. Safety Analysis

Adverse Events (AEs): Summarized by type, frequency, and severity. Fisher's exact test will be used to compare AE rates between groups.

Specific Safety Parameters: Monitoring for hypotension, electrolyte imbalances, and kidney function.

10. Data Quality and Management

Data Quality Measures: Includes data verification, regular audits, and query resolution.

Database Lock: Data will be locked and verified prior to the final analysis.

11. Software

Statistical Software: All analyses will be conducted using SPSS (Version 25).

12. Appendices

	Control group. (n= 41)	Study group. (n= 38)	P value

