BNP: Brain natriuretic peptide; EF: Ejection fraction; LAD: Left atrial dimension; ESV: End-systolic volume; EDV: End diastolic volume; (Student T test or Mann-Whitney) for continuous data, and chi-square test for categorical data. Continuous data are expressed as mean (SD) or median (minimum – maximum). Categorical data are expressed as number (percentage).; Level of significance < 0.05.

Table (6): Comparison between study and control groups as regard effect of intervention on
 disease activity and renal affection at different time points

	Grouping	Baseline	3 months	6 months	9 months	12 months	P value*
Consumed C3 & C4	Control	5 (12.2%)	5 (12.2%)	4 (9.8%)	6 (14.6%)	10 (24.4%)	0.1
No. (%)	Study	2 (5.3%)	5 (13.2%)	2 (5.3%)	6 (15.8%)	6 (15.8%)	0.1
	P value**	0.4	0.9	0.3	1	0.4	
S. creatinine (mg/dL)	Control	0.8 (0.4, 2.7)	0.9 (0.4, 3.1)	0.9 (0.3- 3.1)	0.9 (0.6, 4)	0.9 (0.6, 5)	0.1
Median (min, max)	Study	0.8 (0.4, 2.6)	0.9 (0.6, 2.6)	0.9 (0.5, 3.1)	1 (0.5, 4.2) a	0.9 (0.5, 5)	0.01
	P value**	0.8	0.8	1	0.5	0.8	
eGFR (ml/min/m²) Mean ± SD	Control	114±51	104±45 a	107±53.8	99±47 a	100.3±44.5 a	0.003
	Study	128±59.7	115±47 A	118±50 A	109±44.5 a, c	115.7±48 a	0.001
	P value**	0.6	0.9	0.8	0.2	0.9	
	Control	0.4(0.06- 3.6)	0.6 (0.03-5)	0.6 (0.03- 7)	0.6 (0.02, 5)	0.5 (0.02 , 8)	0.06
24- hour urinary protein (g/24 hours) Median (min, max)	Study	0.6 (0.07-3)	0.7 (0.01-4)	0.8 (0.02, 4.8)	0.6 (0.05, 4.7)	0.5 (0.02 , 4)	0.07
	P value**	0.3	0.9	0.8	0.6	0.6	
Albumin (g/dL)	Control	3.7±0.4	3.7±0.4	3.6±0.4	3.8±0.4 c	3.9±0.3 a, b, c	0.001
iviean ± SD.	Study	3.7±0.3	3.7±0.5	3.7±0.3	3.8±0.3 c	3.9±0.8 a, c	0.04
	P value**	0.4	0.9	0.1	0.7	0.8	

(*) Within group analysis (repeated measure ANOVA).

(**) Between group analysis (Student T test or Mann-Whitney) for continuous data, and chi-square test for categorical data. Post-hoc analysis;

(a) significance against baseline <0.05; (b) significance against 3 months level <0.05, (c) significance against 6 months level <0.05, (d)

significance against 9 months level <0.05. Continuous data are expressed as mean (SD) or median (minimum – maximum). Categorical data are expressed as number (percentage).

Table (7): effect of intervention on hematological findings between both groups at different time points:

	Grouping	Baseline	3 months	6 months	9 months	12 months	P value*
Haemoglobin (g/dL) Mean ± SD	Control	11.9±1.9	12.2±1.9	11.8±2.5	12±1.9	12.2±1.9	0.08
	Study	11.8±1.8	12.3±1.7	12±2.5	11.9±2.2	12±2	0.06

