	P value**	0.5	0.7	0.7	0.3	0.6	
MCV (FL) Mean ± SD	Control	82±7	83±7	84±7	84.6±7.9	81.5±13	0.1
	Study	84±6.9	80±14	83±10	83.2±10.8	84±7	0.3
	P value**	0.9	0.1	0.5	0.5	0.4	
MCH (Pg) Mean ± SD	Control	25.4±2.9	27.3±9.8	28.5±9	26.9±3.2	26.9±3.1	0.08
	Study	26.3±2.9	27.3±9.5	27±3	26.6±3.5	27.1±3.4	0.8
	P value**	0.9	0.9	0.4	0.4	0.5	

(*) Within group analysis (repeated measure ANOVA).

(**) Between group analysis (Student T test or Mann-Whitney) for continuous data, and chi-square test for categorical data. Continuous data are expressed as mean (SD) or median (minimum – maximum). Categorical data are expressed as number (percentage).

MCV: Mean corpuscle volume; MCH: Mean corpuscular haemoglobin.

Table (8): other hematological findings differences between both groups:

	Grouping	Baseline	12 months	P value*
Ferritin (mg/dL)	Control	60 (13, 1113)	75 (6, 2127)	0.5
Median (min, max)	Study	33.5 (3, 1460)	64 (3, 1311)	0.8
	P value**	0.09	0.4	
TSAT (%) Median	Control	23.8 (7, 64)	28 (5, 62)	0.1
	Study	18 (6, 74)	20 (6, 66)	0.9
	P value**	0.05	0.1	
Erythropoietin	Control	11.6±2.1	12.8 ± 3.5	0.08
SD	Study	11.3±1.4	12.4 ± 3.5	0.1
	P value**	0.1	0.6	
Hepcidin level ug/L	Control	198 ± 74	128 ±63	0.001
Mean ± SD	Study	182±76	116±15	0.001
	P value**	0.3	0.2	
Platelet count	Control	288 ± 71	283 ± 74	0.6
(×10³) Mean ± SD	Study	300 ± 79	276 ± 65	0.01
	P value**	0.7	0.5	

(*) Within group analysis (paired t test).

(**) Between group analysis (Student T test or Mann-Whitney) for continuous data, and chi-square test for categorical data.

Continuous data are expressed as mean (SD) or median (minimum – maximum). Categorical data are expressed as number (percentage).

TSAT: Transferrin saturation test

Table (9): Cardiac evaluation differences between both groups after 12 months:

	Control group	Study group	P value
Coronary calcification No. (%)	1 (2.4%)	11 (28.9%)	0.001
Coronary calcification severity No. (%) - No - Minimal - Mild - moderate	40 (97.6%) 0 0 1 (2.4%)	27 (71.1%) 9 (23.7%) 2 (5.3%) 0	0.002
BNP ng/L Mean \pm Sd	66 ± 22.1	65.8±21	0.9
Echocardiographic findi	ng		
EF % Mean ± SD	65.5±5.8	64.9±5.2	0.8
LAD ml Mean \pm SD	26.7±7.6	28.2±8.6	0.4
Aortic diameter ml Mean ± SD	26.6±6.5	25.5±6.2	0.4
ESV ml/min Mean ± SD	39.5±18	36.3±9.3	0.3
EDV ml/min Mean ± SD	108±29.6	109±19.3	0.9

BNP: Brain natriuretic peptide; EF: Ejection fraction; LAD: Left atrial dimension; ESV: End- systolic volume; EDV:

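### SAP 7 assigns LOCF to data missing at random and keeps multiple imputation for an undefined level of missingness; LOCF is not valid under that assumption and distorts estimated change and its interval

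*SAP*

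**What the plan says.** SAP 7 has two lines. The first is the rule: "Last observation carried forward (LOCF) for data missing at random; multiple imputation for extensive missing data". The second describes the sensitivity analysis: "Conducted to evaluate the robustness of primary endpoint findings against different missing data assumptions". The SAP gives no percentage, variable or visit level for extensive missingness, and no imputation model or pooling rule. It also names no sensitivity method. The protocol has no imputation rule.

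The rule feeds these analyses in SAP 6:
- Renal: "ANOVA for repeated measures for serum creatinine and eGFR if normally distributed", otherwise Friedman. Both need a complete row per patient.
- Haematological: "Paired t-test for hemoglobin and erythropoietin levels if data is normally distributed; otherwise, Wilcoxon signed-rank test".
- Cardiovascular: "Mann-Whitney U test for BNP levels and coronary calcification between groups".

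The ITT set is all randomised patients, so each patient with a missing value needs a rule. SAP 4 schedules hepcidin, a primary endpoint, only before and after the intervention. Erythropoietin and BNP are tabulated only at baseline and 12 months (appendix Tables 4, 5, 8 and 9).

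**The concern.** LOCF is tied to the one assumption that does not justify it. MAR says that missingness depends only on observed data. It does not say that the outcome stays where it was last seen. Multiple imputation, which is valid under MAR when its model is adequate, is held back for a case the SAP does not define. The two conditions also overlap: data can be both missing at random and extensive, and the SAP does not say which rule then applies.

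Two things are at stake. The estimated change and its interval may be wrong for endpoints with carried values. The choice of method is also left to the analyst: SAP 2 puts the end of conduct at November 2023, the SAP is dated 2024, and results are appended, so an undefined condition can be settled with the data in view.

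**Working it through.** SAP 7 states no figure to reproduce. The inputs are the tabulated means and SDs. Every dropout share is an assumption.

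**1. Is the course flat?** From appendix Table 6 ("Comparison between study and control groups as regard effect of intervention on" disease activity and renal affection) and Table 8 ("other hematological findings differences between both groups"):

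| Mean | Baseline | 3 m | 6 m | 9 m | 12 m |
|---|---|---|---|---|---|
| eGFR, control | 114 | 104 | 107 | 99 | 100.3 |
| eGFR, study | 128 | 115 | 118 | 109 | 115.7 |
| Hepcidin, control | 198 | – | – | – | 128 |
| Hepcidin, study | 182 | – | – | – | 116 |

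The course is not flat, although most of the study-arm eGFR fall comes by 3 months.

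**2. Within-arm change, two-point endpoint.** Each carried value is the baseline value, so it imputes zero change. If a fraction d is missing and dropouts would have followed their arm's mean, the LOCF change is (1 - d) × true change.
- d = 20%: control hepcidin -70 × 0.80 = -56; study -66 × 0.80 = -52.8.
- d = 18% control and 24% study, the shares that would arise only if 100 were randomised 50:50 and 41 and 38 completed (9/50 and 12/50): hepcidin -70 × 0.82 = -57.4 and -66 × 0.76 = -50.2; erythropoietin +1.2 × 0.82 = +0.98 and +1.1 × 0.76 = +0.84.

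**3. Standard error.** Let m be the mean change, s² = SD₀² + SD₁₂² - 2r·SD₀·SD₁₂, and r the assumed baseline-to-12-month correlation. The ratio of the LOCF to the completers' standard error is (1 - d) × √(1 + d·m²/s²).
- Erythropoietin, r from 0 to 0.9: control (SDs 2.1, 3.5; d = 0.18) 0.826 to 0.850; study (SDs 1.4, 3.5; d = 0.24) 0.768 to 0.780. The interval is too narrow. In simulation at r = 0.5, a nominal 95% interval covered 91.7% and 89.4%.
- Control hepcidin (SDs 74, 63; d = 0.18): 0.857 at r = 0, but 1.11 at r = 0.9. Here the interval can be wider than the completers' interval.

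**4. Paired t statistic.** Dividing step 2 by step 3 cancels (1 - d), so t is multiplied by 1/√(1 + d·m²/s²). For erythropoietin this is 0.992 to 0.964 (control) and 0.990 to 0.974 (study), a fall of about 1-4%.

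**5. Between-arm error (study minus control).** Error = d_study × (carried mean - 12-month mean, study) - d_control × (same, control). All dropouts are taken to leave at the same visit in both arms.

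| Assumed d, control/study | eGFR, value carried from 0 / 3 / 6 / 9 m | Hepcidin |
|---|---|---|
| 18% / 24% | +0.49 / -0.83 / -0.65 / -1.37 | 0.24 × 66 - 0.18 × 70 = +3.24 |
| 20% / 20% | -0.28 / -0.88 / -0.88 / -1.08 | 0.20 × 66 - 0.20 × 70 = -0.8 |

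The standard error of the difference in change, for r from 0.9 to 0.5, is 5.55 to 11.64 (eGFR) and 11.38 to 15.64 (hepcidin). The largest ratios are 1.37/5.55 = 0.25 and 3.24/11.38 = 0.28.

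**6. Dropout that depends on observed eGFR.** Steps 2 to 5 do not let dropout depend on the outcome. A simulation with 400,000 patients per arm used the Table 6 means and SDs, an assumed correlation of 0.70 between adjacent visits, and dropout driven by the previous observed value. The true 12-month difference was about 15.4.
- 16% missing in control and 33% in study: LOCF gave 12.73 against 15.41 (error -2.7).
- Shares reversed: 16.27 against 15.43 (error +0.8).
- Imputation under MAR stayed within about 0.1 of the truth in both cases.

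For scale, the standard error of the 12-month difference is √(44.5²/41 + 48²/38) = 10.4, so 2.7 is about 0.26 of it.

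**The case against.** The strongest reply is that little follows in practice, and much of it stands.
- **The planned tests barely move.** A reader might infer that LOCF materially weakens the paired test of erythropoietin. Step 4 shows that it does not.
- **Intervals are not always too narrow.** That is a tempting general statement, but control hepcidin at r = 0.9 is a counterexample.
- **The two-point schedule is stated only for hepcidin.** For erythropoietin and BNP it is inferred from the tables. The protocol places cardiovascular assessment, including NCCT calcification, under "All patients will be evaluated monthly regarding", so zero imputed change cannot be asserted for calcification.
- **Not every endpoint moved.** The within-arm p values are 0.06 to 0.1 for haemoglobin and erythropoietin, and 0.06 and 0.07 for 24-hour protein.
- **No dropout is documented.** The flow chart (Figure 1) is not shown in the text available. Table 6 uses 41 and 38 as denominators at both baseline and 12 months (10/41 = 24.4%, 6/38 = 15.8%), which fits no dropout, completers only, or filled-in values.

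Two replies do not stand. The per-protocol set of completers avoids most imputation, but the SAP does not offer it as the missing-data check, and completers are themselves biased under MAR: in the first case of step 6 they gave 18.4 against 15.4. Nor is a mixed model a gratuitous change of analysis. The planned repeated-measures ANOVA and Friedman tests need complete rows, so they cannot be run on all randomised patients without some fill-in.

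**Conclusion.** The rule as written is wrong and should be corrected. LOCF is not valid under MAR, the condition for multiple imputation is undefined, and a sensitivity analysis with no named method does not repair the main rule. Confidence is high on the rule and low on the size of its effect.

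The harm falls on the estimate and its interval, and not mainly on the p-value. Within-arm change shrinks by the missing fraction for two-point endpoints if dropouts follow their arm's mean, and the interval does not reflect the imputation. The between-arm error is at most about 0.3 standard errors in these scenarios and can go either way, so LOCF cannot be defended as conservative. All of this is zero if nobody was lost.

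A reader might infer from the target of 100 and the 79 tabulated that 21 patients dropped out, or that tabulated values were carried forward. The documents show neither. The study-arm hepcidin SD of 15 at 12 months and the loss-to-follow-up wording in protocol exclusion 4 are separate queries and play no part in this conclusion.

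**What to change.** In SAP 7, delete LOCF and the condition on extensive missingness, and state instead:
1. **Multi-visit endpoints** (eGFR, creatinine, 24-hour protein, haemoglobin): a likelihood-based mixed model for repeated measures on all observed visits, with a log scale for skewed variables.
2. **Endpoints with only baseline and 12-month values:** multiple imputation at any level of missingness. The model should include arm, baseline value, age, gender and available post-baseline visit data. State the number of imputations and the pooling rule.
3. **BNP and calcification:** keep the planned Mann-Whitney comparison.
4. **Sensitivity analysis:** name delta-adjusted multiple imputation.
5. **Reporting:** give missing counts by arm, endpoint and visit.

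Re-run only endpoints that have missing or carried-forward values, and label the change post hoc, because the study has ended and results are tabulated. The cost is SAP wording, a count of missing values and perhaps a few re-analyses. Intervals will be somewhat wider in most cases, and log-scale results are harder to read. If nothing was missing or carried forward, only the wording and the counts change.

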Statistical Analysis Plan

Document Control

Title: Statistical Analysis Plan for the Study of SGLT2 Inhibitors in Lupus Nephritis Patients

Protocol ID: [NCT05748925] Version: 1.0 Date: [11/3/2024] Principal Investigator: [[name]] Statistician: [[name]] Approval Signatures: Principal Investigator: [name] Statistician: [name]

Table of Contents

- 1. Introduction
- 2. Study Design
- 3. Study Objectives
- 4. Endpoints
- 5. Sample Size Justification
- 6. Statistical Methods
- 7. Handling of Missing Data
- 8. Interim Analysis
- 9. Safety Analysis
- 10. Data Quality and Management
- 11. Software
- 12. Appendices

1. Introduction

• **Purpose of the SAP**: This document outlines the statistical approach for analyzing data from the clinical trial studying the effects of SGLT2 inhibitors on renal, cardiovascular, and hematological outcomes in lupus nephritis patients.

2. Study Design

Design: Randomized, double-blind, placebo-controlled clinical trial.

Study Duration: Conducted from September 2022 to November 2023

Randomization: Patients were randomly assigned to either dapagliflozin (10 mg once daily) or placebo groups using computer-generated random tables in a 1:1 ratio stratified by age and gender.

Blinding: The study was double-blinded, and all trial staff and participants remained unaware of individual treatment assignments until study completion.

3. Study Objectives

Primary Objective: To evaluate the impact of SGLT2 inhibitors on renal, cardiovascular, and hematological parameters in lupus nephritis patients.

Secondary Objective: To explore changes in body weight, BMI, and other echocardiographic and iron profile parameters over 12 months.

4. Endpoints

Primary Endpoints

Renal Function: Serum creatinine, eGFR, and 24-hour urine protein

Cardiovascular Health: BNP levels and coronary calcification via NCCT

Hematological Parameters: Hemoglobin and erythropoietin levels

Hepcidin Level: Measured before and after intervention

Secondary Endpoints

Body Weight and BMI: Assessed at baseline and follow-up visits.

Echocardiographic Findings: Assessed pre- and post-intervention.

Iron Profile: Serum ferritin and TSAT

5. Sample Size Justification

Calculation: A sample size of 100 patients was targeted, accounting for potential dropouts, to provide sufficient power (80%) at a significance level of 0.05 to detect differences between the two groups.

6. Statistical Methods

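### SAP 7 falls back on multiple imputation without a pooling rule, and four of the five primary tests in SAP 6 give no estimate with a standard error that Rubin's rules could combine directly

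*SAP*

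**What the plan says.** SAP 7 (Handling of Missing Data) has one sentence on imputation: LOCF where values are taken to be missing at random, and "multiple imputation for extensive missing data". It adds a sensitivity analysis, "Conducted to evaluate the robustness of primary endpoint findings against different missing data assumptions", without naming a method. It does not say when missingness counts as extensive, which imputation model is used, how many data sets are created, or how their results are combined. The protocol's Statistical Analysis section does not mention missing data.

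SAP 6 names these primary analyses:
- Creatinine and eGFR: repeated-measures ANOVA if normally distributed, and "the Friedman test for non-normally distributed data".
- BNP and calcification: "Mann-Whitney U test for BNP levels and coronary calcification between groups".
- Hemoglobin and erythropoietin: paired t-test, or Wilcoxon signed-rank if not normal.

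No test is named for 24-hour urine protein or hepcidin, although SAP 4 lists both as primary. No effect estimate or confidence interval is named for any primary endpoint. The level is fixed: "A two-sided alpha level of 0.05 will be used for all primary analyses". The ITT population is every randomized patient, so missing outcomes have to be dealt with somehow.

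**The concern.** Multiple imputation produces several completed data sets and therefore several results. Rubin's rules turn them into one, but they need an estimate and its standard error from each set. Among the five named tests only the paired t-test supplies these as it stands. For creatinine, eGFR, BNP and calcification, an analyst who follows the plan has one p-value per imputed set and no written way to a single answer. The normality condition adds a second gap: imputed sets could fall on different sides of it, and the SAP does not say what happens then.

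An unwritten step gets filled by improvisation. Two natural improvisations are to test a single imputed set or to average the imputed values into one set. Both treat imputed values as if they had been observed, which makes p-values too small. What is at stake is the 5% level of the primary tests in the very situation that imputation is meant to protect. A choice among shortcuts after seeing results is also possible.

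**Working it through.** **Inputs from the documents.** Two-sided alpha 0.05 (SAP 6); 100 patients targeted, 80% power (SAP 5); 1:1 allocation (SAP 2), so 50 per arm; 12-month follow-up (Protocol, Patients and methods); 41 control and 38 study patients tabulated (SAP 12).

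**Assumptions, not in the documents.** Missing share 10%, 21% and 40%. The middle value is (100 − 79)/100, where 79 = 41 + 38. Also assumed: the baseline-to-outcome correlation, the number of imputations M, and normal data.

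**The plan's own figures.** The sample size statement is "A sample size of 100 patients was targeted, accounting for potential dropouts, to provide sufficient power (80%) at a significance level of 0.05". It gives no effect size, SD or dropout rate, so 100 cannot be reproduced. It can only be solved backwards: d = (1.960 + 0.842) × √(1/50 + 1/50) = 0.56 SD at 50 per arm, and 2.802 × √(1/41 + 1/38) = 0.63 SD at 41 and 38. The 5% level can be checked: with complete data and no true effect, the four tests rejected in 4.2 to 6.0% of simulated trials.

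**Valid pooling.**
- Estimate Q with variance W in each set: pooled Q̄ = mean of Q; total variance T = W̄ + (1 + 1/M)B, where B is the variance of Q between sets.
- Rank test: use its standardized statistic z as Q, with W = 1, so T = 1 + (1 + 1/M)B.
- Friedman or ANOVA (statistic w on k df), the D2 rule: D2 = [w̄/k − ((M + 1)/(M − 1)) r]/(1 + r), with r = (1 + 1/M) × variance of √w between sets, referred to an F distribution.

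**Error rates.** Null true, 50 per arm, M = 20, regression imputation within arm, 21% missing at random. Mann-Whitney and Wilcoxon: correlation 0.6, 4,000 runs. Friedman and the ANOVA group-by-time test: 5 visits, correlation 0.7, 1,200 runs. Monte Carlo SE near 5% is about 0.3 and 0.6 points respectively. Rejection rate at nominal 5%:

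| Handling | Mann-Whitney | Wilcoxon | Friedman | RM-ANOVA |
|---|---|---|---|---|
| Complete data | 5.2 | 5.2 | 5.1 | 6.0 |
| One imputed set | 11.2 | 11.9 | 12.3 | 15.2 |
| Averaged values | 12.5 | 13.3 | 23.1 | 15.1 |
| Median p | 8.5 | 8.6 | 9.3 | 12.1 |
| Mean p | 5.7 | 5.3 | 6.3 | 8.2 |
| Stacked sets | 70.0 | 69.4 | 98.2 | 98.9 |
| Rubin on z, or D2 | 5.5 | 5.1 | 3.9 | 4.6 |

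**Range.** One imputed set gives 7.6 to 8.4% at 10% missing and 18.0 to 33.5% at 40%. Valid pooling stays at 3.7 to 5.5% from 10 to 40% missing. With 21% missing at purely random positions, M = 10 and correlation 0.3 to 0.8 (3,000 runs), Mann-Whitney gave 7.6 to 10.5% on one set and 7.4 to 13.5% on averaged values. A separate run at 50 per arm and 21% missing gave 7.3 to 9.6% and 7.5 to 13.4%, with Rubin on z at 3.8 to 4.4%. A linear model adjusted for baseline and pooled by Rubin's rules gave 4.0 to 4.9%.

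**Power at 0.5 SD, correlation 0.6, 21% missing.** Mann-Whitney on observed values 56%; adjusted model pooled over imputations 74%; adjusted model on observed values only 77%. Arithmetic explains this. Adjustment shrinks the residual SD to √(1 − 0.6²) = 0.8, so the effect becomes 0.5/0.8 = 0.625 SD. With 79/2 = 39.5 observed per arm, the expected z rises from 0.5 × √(39.5/2) = 2.22 to 0.625 × 4.44 = 2.78. The gain comes from the baseline covariate; imputation adds nothing to it.

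**The case against.** The strongest reply is that the plan contains a gap and not a contradiction. All four tests can be pooled validly, and silence on pooling in a short SAP may be only a request for detail. This stands to the following extent: a reader might infer that imputation combined with these tests can give no valid p-value, and that is wrong, as the last row of the table shows. Nor does every shortcut inflate: the mean p stayed at 4.5 to 5.7% for Mann-Whitney and Wilcoxon, although it reached 11.1% for Friedman and 13.8% for ANOVA at 40% missing.

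Second, nothing in the SAP says that one set would be tested or values averaged, and the problem arises only if imputation is invoked. Both points stand, so the concern is conditional.

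Third, 21% is targeted against tabulated patients. It is not a count of missing 12-month values. The tables show 41 and 38 already at baseline, and the 12-month calcification counts are still full (40 + 1 = 41; 27 + 9 + 2 = 38). The protocol lists loss to follow-up among its exclusions, and no table mentions imputation. A reader should not infer that the tabulated p-values carry this inflation; the documents do not show that.

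Fourth, Friedman, Wilcoxon and the paired t-test are within-subject tests, and the footnote to Table 6 uses repeated-measures ANOVA within group. Their lack of a between-arm estimate is not caused by imputation, and a pooling rule alone would not cure it. That is correct, and it is why the fix goes further than a pooling rule.

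**Conclusion.** The concern holds as an unspecified step with a measurable risk. SAP 7 names multiple imputation without a pooling rule, and four of the five primary tests do not deliver what Rubin's rules use. If imputation is invoked and the analyst improvises with one imputed set or averaged values, the error rate at nominal 5% is about 7 to 15%, up to 23% for Friedman on averaged values, at an assumed 21% missing. It would be lower with less missing data and higher with more. A named valid method keeps it at about 4 to 5.5%.

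The figures rest on normal data, 50 per arm, and the missing shares and correlations stated above. They do not describe a sparse, heavily tied endpoint such as calcification grade. The rise in power from about 56% to 74% belongs to baseline adjustment and is no argument for imputation. The announced sensitivity analysis does not close the gap, because it has no method either.

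**What to change.** In SAP 6 and 7:

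- **Continuous primary endpoints.** In each imputed set, regress the 12-month value on arm and baseline value, using the log scale for BNP, creatinine and urine protein. Pool the arm coefficients and standard errors by Rubin's rules, and report estimate, 95% CI and p. This also removes the normality switch and gives a between-arm comparison.
- **Coronary calcification.** Do not rely on a linear 0 to 3 score, since 40 of 41 controls are graded *No* at 12 months (Table 9). Pre-specify Rubin pooling of the standardized rank statistic, preferably on change from baseline or stratified by baseline grade, because calcification was already 3/41 (7.3%) versus 11/38 (28.9%) at baseline (Table 5). With only 3 calcified controls at baseline, strata may have to be collapsed to absent or present.
- **Specification.** State the trigger for imputation, the imputation model and the number of imputations.
- **Supportive analysis.** Keep the named rank tests on observed values. If any is to be run on imputed data, name Rubin pooling of z or D2.
- **Reporting.** State the number randomized and the number missing per endpoint and arm, so that the real exposure to this problem is known.

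The cost is SAP wording and a re-run on data already collected. The downside is that a model on the log scale replaces a distribution-free test. Because SAP 12 already shows results, the change should be dated and labelled as made after the data were seen.

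### SAP section 8 allows an efficacy stop at 6 months that cannot be tested for three, or on the tables four, of the eight primary endpoints, and it gives no final threshold

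*SAP*

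**What the plan says.** SAP section 8 states: "An interim analysis is planned at the halfway point (6 months". An O'Brien-Fleming approach is to adjust the threshold for the interim test, and the trial may stop early on efficacy or safety grounds. The section does not say which endpoint would trigger a stop, how much information 6 months represents, what the interim boundary is, or what threshold applies at the end.

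SAP section 4 names eight primary endpoints in four groups, with no order among them. Three are renal (creatinine, eGFR and 24-hour protein), two are cardiovascular (BNP and calcification on NCCT), two are hematological (hemoglobin and erythropoietin), and the eighth is hepcidin. Among these eight, only hepcidin is given measurement times there: "Hepcidin Level: Measured before and after intervention".

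SAP section 6 sets the level: "A two-sided alpha level of 0.05 will be used for all primary analyses". The Protocol mentions no interim analysis.

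**The concern.** A stopping rule needs a statistic at the time of the look. Several primaries appear to have none at 6 months. If the rule were followed and the trial stopped for efficacy, those endpoints would be left with a baseline value and no follow-up value, although SAP section 4 ranks them equally with the rest.

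The second question is the error rate. Section 8 adjusts the interim threshold only, and section 6 gives 0.05 for every primary analysis. Taken literally, some alpha is used at 6 months and the full 0.05 is used again at 12 months.

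The status of the look is also unclear. The SAP is dated 2024, gives a study end of November 2023 and already contains 12-month results, yet it describes the interim as planned. A reader cannot tell whether anyone looked, and so cannot tell which threshold the 12-month p-values should meet.

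**Working it through.** **Step 1. Which primaries have 6-month data?** The table sets SAP section 4 against the SAP appendix tables and the Protocol's monthly after-intervention list.

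| Primary endpoint | 6-month value in SAP tables | 6-month measurement in the plan text |
|---|---|---|
| Serum creatinine | Yes (Table 6) | Yes, monthly list |
| eGFR | Yes (Table 6) | Yes, through monthly creatinine and clearance |
| 24-hour urine protein | Yes (Table 6) | Yes, monthly list |
| Hemoglobin | Yes (Table 7) | Yes, monthly list |
| Coronary calcification | No: baseline (Table 5) and 12 months (Table 9) | Nominally: NCCT vascular calcification is under item 9 of the monthly list |
| BNP | No: baseline (Table 5) and 12 months (Table 9) | None |
| Erythropoietin | No: baseline and 12 months (Table 8) | None |
| Hepcidin | No: baseline and 12 months (Table 8) | None; SAP section 4 fixes before and after only |

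Table 9, the only follow-up source for BNP and calcification, is titled "Cardiac evaluation differences between both groups after 12 months". The count without a 6-month value is 4 of 8 on the tables and 3 of 8 on the plan text. The difference is coronary calcification, where the Protocol's monthly list and the SAP tables must be reconciled.

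Of the four with 6-month data, hemoglobin is assigned a paired within-group test in SAP section 6. That test gives no between-arm statistic to compare with a boundary.

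**Step 2. What total alpha results for an endpoint tested twice?** The SAP's figure is 0.05 two-sided. It gives no boundary and no information fraction, so I assume t = 0.5.

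Let Z1 and Z2 be the interim and final statistics, bivariate normal under the null with correlation √t = √0.5 = 0.707. The total error is 1 − P(|Z1| < c1 and |Z2| < c2).

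- Classic O'Brien-Fleming: c1 = c2/√t. Solving for a total of 0.05 gives c2 = 1.977 (p = 0.0480) and c1 = 1.977/0.707 = 2.797 (p = 0.0052).
- Lan-DeMets spending of O'Brien-Fleming type: alpha spent at the interim is 4[1 − Φ(z(0.9875)/√t)] = 0.0031, so c1 = 2.963. Solving for the remainder gives c2 = 1.969 (p = 0.0490).

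With these final thresholds the total is 0.0500, which reproduces the SAP's figure. Setting the final threshold back to 0.05 (c2 = 1.960) gives:

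| Boundary | Interim p | Final p | Total |
|---|---|---|---|
| Classic, final adjusted | 0.0052 | 0.0480 | 0.0500 |
| Classic, final at 0.05 | 0.0052 | 0.0500 | 0.0520 |
| Lan-DeMets, final adjusted | 0.0031 | 0.0490 | 0.0500 |
| Lan-DeMets, final at 0.05 | 0.0031 | 0.0500 | 0.0510 |

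The excess is 0.001 to 0.002 per endpoint with two looks. An endpoint with a single 12-month look stays at 0.0500.

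**Step 3. How far does this depend on the assumption?** With the classic interim boundary held and the final at 0.05, the total runs from 0.0549 at correlation 0 to 0.0502 at correlation 0.9. The excess stays small throughout.

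**The case against.** The best defence is that section 8 is thin rather than wrong. A group-sequential plan normally quotes the overall alpha, and O'Brien-Fleming then preserves it, so the 0.05 in section 6 may be that overall level. This stands: the documents do not decide between the two readings, and what can be said is that the final threshold is not stated.

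An interim also need not test every primary. That is true, but the SAP would then have to name the endpoint that governs a stop, and it does not. Stopping on one endpoint would still end collection for those measured only at 12 months.

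Absence from a results table does not prove that nothing was measured. This stands for coronary calcification, hence the two counts. It does not help BNP, erythropoietin or hepcidin, which have no 6-month schedule in either document.

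The reported results show no practical consequence. The 6-month between-group p-values are 1 (creatinine), 0.8 (eGFR), 0.8 (urine protein) and 0.7 (hemoglobin), and no reported 12-month p-value for a primary lies between 0.048 and 0.05. This also stands. It limits the damage, but it does not tell the reader whether a look took place.

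**Conclusion.** The point holds as a defect in the stopping rule. SAP section 8 permits an efficacy stop that cannot be tested for 3 of 8 primaries on the plan text, or 4 of 8 on the tables, and that would forfeit their only reported post-baseline value. The alpha part is secondary: 0.051 to 0.052 instead of 0.05 per endpoint with two looks, on the literal reading and assuming half the information at 6 months. It should be corrected, but it does not overturn any reported result.

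A reader might infer more than the documents support:

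- That the interim causes a large false-positive rate. It adds 0.001 to 0.002 per endpoint. The absence of any adjustment across eight primaries is a separate issue that exists with or without an interim.
- That an efficacy look contradicts the blinding. SAP section 2 says "all trial staff and participants remained unaware of individual treatment assignments until study completion". A comparison by coded arm need not reveal individual assignments. The SAP is silent on who would make the look, and silence is not contradiction.
- That the look was pointless because enrolment was over. September 2022 to November 2023 is 14 to 15 months, and 12 months of follow-up leaves 2 to 3 for recruitment, so a stop would save no enrolment. It could still shorten follow-up, so this is not an error in itself.
- That a look was in fact taken. Nothing in the documents shows this either way.

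**What to change.** State in SAP section 8 whether an efficacy look was taken at 6 months.

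- If none was taken: say so, delete the efficacy stop, keep the 6-month safety monitoring, and keep 0.05 at the final analysis.
- If one was taken: disclose which endpoint or endpoints were actually examined, with the actual information fraction and boundary form. Test those endpoints at the matching final threshold, about 0.048 (classic) or 0.049 (Lan-DeMets) at half information, and amend SAP section 6 to agree. Do not choose an endpoint such as eGFR now, because the results are already in the document and the choice would be post hoc.

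In either case, reconcile the Protocol's monthly NCCT entry with the SAP tables that show calcification only at baseline and 12 months.

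The cost is SAP wording, plus a slightly stricter final threshold for the endpoints concerned if a look occurred.
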